## 6 STUDY PROCEDURES

Tests/procedures will be ordered per the schedule and requirements listed in this section of this protocol. All assessments for eligibility and adverse events must be performed by a study trained and delegated investigator. Investigator assessment of eligibility is performed at time of enrollment and must be specifically documented within the subject's study file.

### 6.1 Consent/Screening

During routine clinical follow-up after Stage I surgery, as Stage II surgery is being planned, the parent(s) and/or legal guardian(s) will be approached by study staff to consider enrollment of their child in this study. See Section 4.2 for additional details pertaining to the pre-screening process. Potential subjects must be pre-screened prior to beginning the consenting process. Information about the study will be provided to the parent(s) and/or legal guardian(s), and adequate time for questions will be allowed prior to signing the consent form. The IRB-approved, study-specific Informed Consent Form and HIPAA Authorization will be signed by both parents, unless one parent and/or legal guardian is not reasonably available. See Section 3.1.1 of this protocol for treatment group assignment.

The following data will be collected *after* consent has been obtained and the data will be entered in the applicable eCRFs and the subject's study file:

#### 6.1.1 Baseline/Pre-Op:

- Medical History
- Concomitant Medications
- Physical Exam (including weight)
- Vital Signs (temperature, heart rate, blood pressure, oxygen saturation)
- Cardiac Markers (CRP, High Sensitivity Troponin T, NT-proBNP)
- CBC w/ Differential (RBC, WBC, Hemoglobin, Hematocrit, Platelets, Neutrophils, Lymphocytes, Monocytes, Eosinophils and Basophils)
- Liver/Renal Function (ALT, ALP, AST, total bilirubin, albumin, total protein, BUN, creatinine)
- TSH
- Panel-Reactive Antibody (PRA) Test (see Appendix D)
- 12 lead ECG
- Cardiac MRI
- Echo (TTE)
- Cardiac Cath (when clinically available)
- Questionnaire Completion

Consent must occur before any study procedures are completed, however standard of care procedures done within 30 days prior to Stage II surgery may be used rather than repeating procedures to collect study data. Standard of care cardiac MRI data may be used if done within 60 days prior to Stage II surgery.

### **6.1.2 Study Timeout (Treatment Group Only):**

Within five days prior to Stage II surgery, the site investigator (cardiac surgeon) performing the cell delivery procedure must complete the Study Timeout form. The UCB-MNC product volume and number of injection sites, based on the pre-operative baseline visit weight, will be calculated and documented. See Section 5.3 for instructions pertaining to dosing calculations. The site investigator should also document assignment of responsibility to all site personnel involved on the day of procedure. The completed Study Timeout form must be available at the time of surgery to ensure the calculated volume of investigational product is prepared for investigational product administration.

### **6.1.3 Stage II Surgery:**

- Changes in Medical History
- Changes in Concomitant Medications
- Physical Exam (including weight)
- Vital Signs (temperature, heart rate, blood pressure, oxygen saturation)

Any new findings/abnormalities identified prior to enrollment will continue to be recorded as medical history unless considered related to a study-related test or procedure.

## **6.2 Enrollment**

### **6.2.1 Enrollment/Cell Delivery:**

- Procedural Timeout (after completion of Stage II surgery)
- Assessment of Eligibility/Enrollment
- AE Assessment
- Cell delivery (treatment group only)
- Telemetry
- High Sensitivity Troponin T at 3 hour +/- 30 min and 6 hour +/- 30 min after enrollment

A site investigator will assess subject eligibility up to the time of enrollment. If there are new test results or conditions identified up to the time of enrollment that causes a subject to no longer be eligible for participation in this study, the subject will be considered a screen failure.

Adverse events will be recorded in the eCRF and subject's study binder following enrollment to document new or worsening symptoms.

During the hospitalization (starting on Day 0), subjects will be monitored with continuous telemetry from enrollment through discharge (or up to 30 days post-surgery if the subject remains hospitalized). The date and time and the type of any arrhythmias that occur via telemetry that are determined to be clinically significant by a study cardiologist will be recorded in the appropriate eCRF and within the subject's study file.

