**CLINICAL STUDY SUMMARY**

Title	Phase IIb Study of Intramyocardial Injection of Autologous Umbilical Cord Blood Derived Mononuclear Cells during Stage II Surgical Repair of Hypoplastic Left Heart Syndrome (AutoCell-II)
Running Title	Phase IIb Efficacy Study of UCB-MNC Intramyocardial Injection for HLHS and HLHS Variants
Protocol Number	CSP-4401
Phase	Phase IIb
Study Design	Prospective, Open label, Non-randomized, Observational Study
Overall Study Duration	6 years
Subject Participation Duration	Up to 4 years or until pre-operative work-up for Stage III surgical palliation has been completed or until cardiac transplant, whichever is first
Single or Multi-Site	Multi-Site
Objectives	This study will evaluate the efficacy and safety of UCB-MNC intramyocardial injections performed during Stage II surgical palliation by focusing on short and long-term cardiac function leading up to the pre-operative work-up for Stage III surgical palliation.
Study Purpose	Determine if the delivery of the autologous UCB-MNC product into the myocardium of the right ventricle of the heart at the time of Stage II surgical repair will provide a short-term improvement in cardiac function, while also providing a reduction in the cumulative days of hospitalization following Stage II surgical repair. Additionally, long-term improvement in cardiac function, growth, reaching Stage III surgical repair pre-op work-up and prolonging time to cardiac transplantation or death will be determined. Reaching developmental milestones and quality of life will also be monitored.
Number of Subjects	30-50 treated subjects receiving cell product, along with 30-50 subjects with standard surgical treatment (not receiving cell product).
Study Population	Subjects less than 13 months of age with HLHS or HLHS variant who are undergoing Stage II surgical palliation.
Study Product, Dose, Route, Regimen	The investigational product is autologous MNC derived from UCB at a concentration of 10-30 million TNC per mL. The investigational product will be delivered into the right myocardium via sub-epicardial injections of 0.1 mL per kg body weight to achieve the target dose of 1-3 million TNC per kg body weight.
Time and Duration of Administration	A single treatment will be administered intraoperatively upon the successful completion of the planned Stage II surgical repair.

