This protocol is designed to evaluate the clinical outcomes following intramyocardial delivery of autologous UCB-MNC and is being conducted to investigate this product and its delivery procedure as a potential new therapy to strengthen the right ventricle of patients with HLHS or HLHS variants. The central hypothesis of this study is that the delivery of the autologous UCB-MNC product into the myocardium of the right ventricle of the heart at the time of Stage II surgical repair will provide a short-term improvement in cardiac function, reaching growth and developmental milestones, and quality of life, while also providing a reduction in the cumulative days of hospitalization following discharge for the Stage II surgical repair. It is also hypothesized that the autologous UCB-MNC product and its delivery procedure will ultimately provide long-term improvement in cardiac function, reaching growth and developmental milestones, reaching Stage III surgical repair pre-operative work-up, prolonging time to cardiac transplantation or death, and improving quality of life.

The safety and efficacy endpoints will be evaluated by the DSMB at least annually. This will determine the appropriateness of continued enrollment in both arms of this Phase IIb study. By demonstrating reasonable efficacy and safety of this product and its delivery procedure in this study, future definitive studies may be designed with the goal to establish a marketable regenerative therapy to treat this rare, life-threatening congenital heart disease as quickly as possible.

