## 2 STUDY OBJECTIVES

The purpose of this Phase IIb clinical study is to evaluate the efficacy and safety of autologous UCB-MNC intramyocardial injections into the single, morphological right ventricle of subjects with HLHS or HLHS variants requiring Stage II surgical repair. Thirty to fifty treated subjects and thirty to fifty control subjects will be accrued. Subjects accrued in the treatment arm (Arm A) of this study will be treated with a single dose following successful completion of Stage II surgical repair. Subjects accrued in the control arm (Arm B) of this study will be followed according to the same protocol requirements as the treatment arm but will not receive cell therapy. In the treatment and control arms, surrogate markers of cardiac function, growth, success in reaching Stage III surgical repair pre-operative work-up, time to cardiac transplantation or death, and cumulative days of hospitalization will be recorded and evaluated following the completion of Stage II surgery for up to four years, or until the pre-operative work-up for the Stage III surgical repair has been completed or until cardiac transplant, whichever is first. Development and quality of life as measured by questionnaires will also be monitored. Follow-up surrogate markers and the other variables noted above that are recorded for this study will be compared to baseline and by study arm. The surrogate markers and other variables are described in Section 3 of this protocol.

The objective is to evaluate the short-term (up through 3 months post-Stage II surgical repair) cardiac function, growth, and cumulative days of hospitalization following discharge for the Stage II surgical repair in the treatment and control arms, adjusting for baseline.

This evaluation will also include long-term (6 months and up to 4 years post-Stage II surgical repair or until the pre-operative work-up for the Stage III surgical repair has been completed or until cardiac transplant), cardiac function, growth, ability to reach Stage III surgical repair pre-operative work-up and time to cardiac transplantation or death in the treatment and control arms, adjusting for baseline.

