 3 Tests/procedures will be performed daily during the hospitalization starting on Day 0. Continuous telemetry is not required on day of hospital discharge.  
 4 Laboratory tests, 12-lead ECG, and echo should be completed within 3 days of the discharge date. However, the laboratory tests, 12-lead ECG, and echo don't have to be repeated if the discharge date changes unexpectedly due to non-cardiac related issues.

- 5 To be conducted at 6 months post-Stage II surgery and every 6 months following the 12 month in-clinic visit for up to 4 years or until pre-operative Stage III work up or cardiac transplant.
- 6 Data to be collected from standard of care Stage III surgery pre-op work up in subject's medical records.
- 7 A subject will be considered enrolled on the study after completion of the procedural time-out.
- 8 Collection of medical history to occur up to enrollment. AE assessments to begin immediately following enrollment.
- 9 During Stage II Surgery hospital stay, changes in concomitant medications will not be recorded.
- 10 Includes weight, except for during post-op hospital stay
- 11 Includes temperature, heart rate, blood pressure and oxygen saturation. Temperature not required at 3 or 12-month in clinic visit.
- 12 Includes the following tests: High Sensitivity Troponin T, CRP, and NT-proBNP. On day 0, only the cardiac biomarker panel (High Sensitivity Troponin T) will be collected at 3 hr  $\pm$  30 min and 6 hr  $\pm$  30 min after enrollment.
- 13 Includes the following tests: RBC, WBC, Hemoglobin, Hematocrit, Platelets, Neutrophils, Lymphocytes, Monocytes, Eosinophils and Basophils
- 14 Includes the following tests: ALT, ALP, AST, Total Bilirubin, Albumin, Total Protein, BUN, and Creatinine.
- 15 Cardiac MRI will only be required at baseline. It is not required at 3 month visit or 12-month follow up. Baseline cardiac MRI should occur within 60 days prior to Stage II surgery.
- 16 When clinically available.
- 17 Questionnaires will be administered to participants at baseline and at 12, 24, 36 and 48 months post Stage II surgery for the duration of a subject's participation in the study.
- 18 Treatment arm only. Must occur within 5 days prior to cell delivery (see Sect. 6.1.2).
- 19 Required for both treatment and control arms (see Sect. 4.3).

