#### **7.4.5 Safety Analysis**

Adverse Events (AEs) will be described by count and frequency, by body system and severity and groups compared using the chi-square test.

The long-term endpoint regarding arrhythmia events and arrhythmia medication will be analyzed regarding safety. Additional adverse events which will be separated out for analyses of their own will be occurrences of bleeding, to such an extent they would be regarded as AEs, decreased cardiac function, and tumor formation.

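### The arrhythmia safety comparison takes no account of telemetry time, which ends at each child's discharge and may differ between arms

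*Combined protocol and SAP*

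**What the plan says.** Section 6.2.1 states that "subjects will be monitored with continuous telemetry from enrollment through discharge (or up to 30 days post-surgery if the subject remains hospitalized". Footnote 3 of the Section 6.5 schedule adds: "Continuous telemetry is not required on day of hospital discharge". Not every telemetry finding is kept. Section 6.2.1 asks for the date, time and type of arrhythmias "that are determined to be clinically significant by a study cardiologist will be recorded in the appropriate eCRF".

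Sections 1.5 and 8.10 list ventricular arrhythmia among the risks of the product. Section 7.4.5 describes adverse events by count and frequency, with "groups compared using the chi-square test". It then says: "The long-term endpoint regarding arrhythmia events and arrhythmia medication will be analyzed regarding safety". Section 3.3 has a long-term endpoint on arrhythmia medication but none on arrhythmia events.

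The hospital-days hypothesis is worded in two ways. The Clinical Study Summary speaks of "providing a reduction in the cumulative days of hospitalization following Stage II surgical repair", and the endpoint in Section 3.2 counts days at 1 and 3 months from surgery. Both can include the Stage II stay itself. Section 1 speaks of a "reduction in the cumulative days of hospitalization following discharge for the Stage II surgical repair", and Section 2 sets as an objective the "cumulative days of hospitalization following discharge for the Stage II surgical repair in the treatment and control arms". Both of these exclude it.

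**The concern.** Continuous telemetry can be expected to detect more arrhythmia than any other assessment in the schedule, and it is the one whose duration varies from child to child. A simple comparison of proportions treats a child watched for one week and a child watched for three as equally observed. If the arms differ in stay, part of any difference in arrhythmia frequency reflects observation time and not risk.

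Stays could differ for several reasons in this design: case mix, site, unblinded discharge decisions, or a treatment effect. If Arm A goes home sooner, the error is towards reassurance and a real excess is harder to see. If Arm A stays longer, the error reverses and the product looks worse than it is.

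**Working it through.** **Plan's own figure.** The documents state no figure for stay, telemetry or arrhythmia. The sample-size statement in Section 7.1 supplies the n used below, so it was checked first. With n per arm = 2(1.96 + 0.842)²/d², d = 0.57 gives 48.3, so 49, and d = 0.74 gives 28.7, so 29. The t-test detectable effects are 0.566 at 50 per arm and 0.736 at 30 per arm (40% attrition). The plan's 0.57 and 0.74 reproduce, two-sided.

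**What else detects arrhythmia.**
- In hospital: daily adverse-event assessment and examination (6.2.2), and a 12-lead ECG around discharge (6.2.3).
- After discharge: adverse-event questioning at 1 month with no ECG (6.3.1). The next scheduled ECG is at 3 months (6.3.2, 6.5).
- Recording: Section 8.8 captures events that are serious, at least possibly related, or at least moderate. A mild arrhythmia judged unrelated need not be recorded as an adverse event.
- In-hospital medication changes are not recorded (4.7), so they cannot serve as a back-up.

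**Spurious difference with equal true risk.** Stays and hazards are assumed. P(at least one detected event) = 1 − exp(−H(t)), where t is the stay. Constant hazard: H(t) = 0.03t. Front-loaded hazard: H(t) = (0.10/k)(1 − exp(−kt)), k = ln 2/half-life.

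| Hazard | 14 v 10 days | 20 v 12 days |
|---|---|---|
| Constant 0.03/day | 34.3% v 25.9% (8.4 points) | 45.1% v 30.2% (14.9 points) |
| 0.10/day, 5-day half-life | 46.1% v 41.8% (4.3 points) | 49.1% v 44.3% (4.9 points) |
| 0.10/day, 2-day half-life | 24.9% v 24.4% (0.5 points) | 25.0% v 24.7% (0.3 points) |

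For example, constant hazard at 20 v 12 days: 1 − exp(−0.60) = 45.1% and 1 − exp(−0.36) = 30.2%.

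**Effect on the chi-square test.** Assumed: 50 per arm, stay in the longer-stay arm 10 days with 20% incidence, no true difference, uncorrected test, exact rejection probabilities.

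| Stay in shorter arm | Constant hazard: incidence (risk ratio) | Falsely lower | Falsely higher | 2-day half-life: risk ratio | Falsely lower |
|---|---|---|---|---|---|
| 10 days | 20.0% (1.00) | 2.6% | 2.6% | 1.00 | 2.6% |
| 9 days | 18.2% (0.91) | 4.4% | 1.5% | 0.99 | 2.8% |
| 8 days | 16.3% (0.82) | 7.2% | 0.8% | 0.97 | 3.1% |
| 7 days | 14.5% (0.72) | 11.5% | 0.4% | 0.95 | 3.5% |
| 5 days | 10.6% (0.53) | 27.1% | 0.1% | 0.86 | 5.6% |

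At 7 v 10 days with constant hazard, varying the longer-stay incidence from 10% to 40% gives risk ratios of 0.71 to 0.75 and a falsely lower result in 7.0% to 17.7%.

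**Candidate remedies.** In a common window during which both arms are fully monitored, H is the same in both arms, so the expected risk ratio is 1.00 for either hazard shape. A rate per telemetry-day gives 1.00 only if the hazard is constant. With a 2-day half-life and stays of 7 v 10 days, cumulative hazard is proportional to 1 − 2^(−3.5) = 0.912 and 1 − 2^(−5) = 0.969. The rate ratio is (0.912/7)/(0.969/10) ≈ 1.34 against the arm discharged sooner, so it over-corrects.

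**The case against.** A reader might infer that the trial expects cells to shorten the Stage II stay, so that Arm A will look safer. The documents do not support that. Sections 1 and 2 place the hoped-for reduction after discharge, when telemetry has already stopped. Only the Summary and the Section 3.2 endpoint leave room for the Stage II stay. No stay by arm is given, and the difference could go either way.

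It is also tempting to say that nothing else watches for arrhythmia. That is not so. The chi-square test applies to adverse events, which are sought by specific questioning at every contact (8.4) on a schedule counted from surgery in both arms. Readmission for arrhythmia would be a serious adverse event (8.2). What an early discharge loses is mainly events that telemetry would show but that are brief or silent at home.

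The larger figures depend on invented inputs. For a single intraoperative injection, risk concentrated in the first days is at least as plausible as constant risk, and the distortion is then small. The enrollment hold in Section 8.11 rests on individual events or on patterns seen by the Sponsor or DSMB, not on a test result. Unadjusted frequencies are also common in small phase II studies.

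All of this stands as a limit on direction and size. It does not remove the gap: monitored time can differ by arm, the plan neither fixes nor reports it, and no ECG is scheduled between discharge and 3 months.

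The arrhythmia-event endpoint missing from Section 3.3 is a separate drafting mismatch. It concerns a long-term endpoint and says little about in-hospital telemetry.

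**Conclusion.** The point holds in conditional form. If the Stage II stay differs between arms, telemetry-detected arrhythmia will differ with no true difference in risk, and Section 7.4.5 has nothing to separate the two. The direction is not established. The range of about 0.3 to 15 percentage points rests wholly on assumed stays and hazards. Within each scenario the figure is an upper bound for the all-adverse-event comparison, because the calculation counts every event after discharge as undetected. With stays of 7 v 10 days and 20% incidence in the longer-stay arm, the chance of a falsely lower result is 11.5% under constant hazard but 3.5% with a 2-day half-life, against 2.6% with equal stays. The change is worth making because it is cheap and concerns a named product risk. It is not evidence that the safety analysis will favour Arm A.

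**What to change.** In Section 7.4.5:

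1. Add a between-arm comparison of telemetry-detected, clinically significant arrhythmias in a fixed early post-operative window in which essentially all children are still monitored, for example enrollment to 72 hours. Report the number still on telemetry at the end of the window in each arm, since the documents give no stays from which to confirm the choice.
2. Keep the all-adverse-event comparison as planned.
3. Report monitored days by arm beside the arrhythmia results.
4. Give an exposure-adjusted rate through discharge or 30 days as a sensitivity analysis only. State that it can over-correct when risk is front-loaded, and that discharge may be informative because a child with an arrhythmia may be kept longer.
5. Either define the arrhythmia-event endpoint and its window in Section 3.3, or limit the sentence in 7.4.5 to arrhythmia medication.

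Separately, reconcile the Summary and Section 3.2 with Sections 1 and 2 on whether hospital days include the Stage II stay.

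Cost: mainly SAP wording. Event dates and times are already recorded, and the hospital-days endpoint already needs stay dates, which give approximate monitored days. Exact exposure would need telemetry start and stop times, which the documents do not list, so that is a small addition to the eCRF. Patient monitoring does not change. The downside is that later in-hospital events do not enter the fixed-window comparison. The window also does not remove confounding from non-randomized assignment or the subjectivity of an open-label judgement of clinical significance.

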### **6.2.2 Post- Op Hospital Stay:**

- AE Assessment
- Physical Exam
- Vital Signs (temperature, heart rate, blood pressure, oxygen saturation)
- Telemetry

The tests/procedures included in the bulleted list above will be performed daily during the hospitalization. Any tests/procedures that are performed, but not listed above, will be for the treatment of the subject according to post-surgical standard of care.

Adverse events will be recorded in the eCRF and subject's study binder following enrollment to document new or worsening symptoms throughout the hospitalization.

### **6.2.3 Hospital Discharge:**

- Changes in Concomitant Medications
- AE Assessment
- Physical Exam (including weight)
- Vital Signs (temperature, heart rate, blood pressure, oxygen saturation)
- Cardiac Markers (CRP, High Sensitivity Troponin T, NT-pro BNP)
- CBC w/ Differential (RBC, WBC, Hemoglobin, Hematocrit, Platelets, Neutrophils, Lymphocytes, Monocytes, Eosinophils and Basophils)
- Liver/Renal Function (ALT, ALP, AST, total bilirubin, albumin, total protein, BUN, creatinine)
- TSH
- 12 Lead ECG
- Echo (TTE)

At the time of discharge from the hospital, the above tests/procedures will be conducted. The laboratory tests, 12-lead ECG, and echo should be completed within 3 days of the final discharge date. However, the laboratory tests, 12-lead ECG, and echo don't have to be repeated if the discharge date changes unexpectedly due to non-cardiac related issues.

